⁴ Griffin KH, Nate KC, Rivard RL, Christianson JB, Dusek JA. Referrals to integrative medicine in a tertiary hospital: findings from electronic health record data and qualitative interviews. BMJ Open. 2016 Jul 25;6(7):e012006. doi: 10.1136/bmjopen-2016-012006.

⁵ Nahin RL, Barnes PM, Stussman BJ. Insurance coverage for complementary health approaches among adult users: United States, 2002 and 2012. NCHS data brief, no 235. Hyattsville, MD: National Center for Health Statistics. 2016.

⁶Fletcher CE, Mitchinson AR, Trumble EL, Hinshaw DB, Dusek JA. Perceptions of other integrative health therapies by Veterans with pain who are receiving massage. J Rehabil Res Dev. 2016;53(1):117-26. doi: 10.1682/JRRD.2015.01.0015.

seem to modulate pain by reducing the level of attention paid to noxious stimuli, thereby suppressing transmission of painful sensations to the cerebral cortex. ^{10,11} When used in addition to usual care (opioid analgesics, with or without non-interactive distraction therapies), VR has been shown to provide clinically and statistically significant reduction in subjective pain score ratings. ^{12,13} The immersive nature of VR makes it a more engaging form of distraction therapy compared to playing a video game or listening to music (e.g. rather than watching a video of a beach, one visually and acoustically experiences being at the beach). Additionally, VR is becoming increasingly portable and affordable with growing availability of thematic content such that patients may select VR experiences that interest them.

Despite growing evidence to the benefit of VR for pain management, no research has yet elucidated its role in outpatients with cancer-related pain.

PURPOSE

The purpose of this research project is to evaluate the impact of virtual reality therapy on mitigating moderate to severe cancer pain in outpatients.

AIMS and HYPOTHESES

Specific Aim 1: To collect and compare pilot data on the impact of a VR intervention against standard care (pre-enrollment analgesic regimen) on pain management measures for outpatients with cancer who have a baseline pain self-rated at least 4/10 (0=no pain, 10=worst pain).

Hypothesis 1: Patients with cancer receiving a virtual reality (VR) intervention will have significantly larger improvements in self-reported pain scores, satisfaction with pain management, lower distress, greater well-being, and lower as-needed opioid use compared to their baseline.

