Because of the nature of the compared interventions, subjects and researchers cannot be blinded to intervention. Our primary outcome measure will determine the impact of VR on self-reported pain score in the last week (numeric rating scale, collected weekly). Self-reported pain experience remains the standard for clinical pain research. Secondary outcomes will measure pain interference (PROMIS Pain Interference Short Form, collected weekly), as-needed opioid use for patients taking opioid analgesics at the time of enrollment (self-reported using medication administration form), satisfaction with VR intervention and overall pain management (collected weekly), and survey of preferences for VR thematic content (collected after Week 4).

Following consent, subjects will complete baseline outcome assessments including self-reported pain score in the last week, the PROMIS Pain Interference Short Form, as-needed opioid use in the last week if applicable, and satisfaction with overall pain management. Subjects will then be provided with a VR headset and paired Touch controllers to bring home for the duration of the study and instructions on the frequency of use for each week. A member of the research will educate the patient on the technology and assure comfort with use. The research study coordinator will contact patients by phone at the end of each week to confirm dates and duration of use as specified by the study protocol, collect self-reported pain score in the last week, the PROMIS Pain Interference Short Form, as-needed opioid use in the last week if applicable, and satisfaction with the VR intervention and overall pain management. Additionally, participants will be surveyed on preferences for VR thematic content at the end of Week 3.

Participants will be monitored for adverse effects and harm for the duration of the study. Although well tolerated in previous studies of patients with cancer and advanced heart failure, potential risks may include dizziness, nausea, eye strain, and loss of confidentiality if data security is breached. Participants are instructed to only utilize the VR device while in a seated or reclined position and to never use the device when standing or ambulating due to the risk of potentially serious injury from falling.

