Participants will be compensated for their time and participation in this research; participants may keep the VR headset assigned to them for the study, and will receive a \$50 gift card upon completing the final survey at the end of Week 3. Participants will not be responsible for replacing or repairing the VR device if it is lost or damaged during the study period; a replacement device will be provided by the research team. Participants who wish to return the device may do so at their next scheduled appointment for usual care at MedStar Washington Hospital Center, where a member of the research team will collect it. Participants will not be required to schedule an appointment or return to MWHC for the purpose of returning the device. Participants who wish to return the device and are

unable or unwilling to return to MWHC for any reason will be provided with a prepaid shipping label by mail to return the device to the research team.

Results of this study will be used to determine the effect size, variance and variability to estimate sample size for a larger study. For this pilot study, a sample size of 60 is sufficient to provide accurate estimates of the information needed to calculate sample size for a future study. In the unanticipated circumstance that we are not able to accrue 60 participants during the study period, we will still be able to perform the desired analysis and calculate sample size for a future study if accrual is as low as 30 participants.

Funding for this study has been obtained through the Palliative Care Research Collaborative investigator Development Pilot Award (https://palliativecareresearch.org). The grant award is \$67,031 to support execution of the study over a 1-year period, beginning July 1 of 2022 and ending June 30, 2023.

DATA COLLECTION

Subjects will record daily use of the VR headset and duration of use for each session on a paper calendar provided to them at the time of enrollment. Subject survey data will be collected and entered by the research study coordinator using an online survey system accessible only to the research team (Tonic Health). Subjects will be assigned a de-identified code for survey entry. All data will be password protected and de-identified prior to analysis. Results will be reported in aggregate.

DATA SAFETY MONITORING PLAN

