Descriptive analyses will be performed to summarize baseline characteristics, including initial pain measures from self-report pain rating scale and PROMIS Pain survey. Preferences for VR thematic content and satisfaction with VR intervention will also be summarized. Summary statistics include frequency (%) for categorical variables and mean, standard deviations, median and IQR (1st and 3rd quartile) for continuous variables. Paired t-test or Wilcoxon sign rank test will be used to compare each

time point (end of weeks 1, 2, and 3) to the baseline (beginning of week 1) regarding pain score and PROMIS survey outcomes. Linear mixed-effects model will be used to assess the trend of pain score over the study period controlling for pain medication usage and other covariates (e.g., age, sex).

Data Collection Plan:

Time of Data Collection	Method of Data Collection+	Data Elements Collected
Beginning of Week 1 (Time of Enrollment)	Patient Survey (all patients)	 Self-reported pain score PROMIS Pain Interference Short Form As-needed opioid use* Satisfaction with overall pain management
End of Week 1	Patient Survey (all patients)	 Self-reported pain score PROMIS Pain Interference Short Form As-needed opioid use* Satisfaction with VR intervention and overall pain management
End of Week 2	Patient Survey (all patients)	 Self-reported pain score PROMIS Pain Interference Short Form As-needed opioid use* Satisfaction with VR intervention and overall pain management
End of Week 3	Patient Survey (all patients)	 Self-reported pain score PROMIS Pain Interference Short Form As-needed opioid use* Satisfaction with VR intervention and overall pain management Preferences for VR thematic content

* Data collected for patients receiving as-needed opioid analgesics at the time study enrollment

+ Patient survey administered by Research Coordinator by phone, data entered into Tonic Health

DATA SHARING

Data collected over the course will include summary findings of N = 60 enrolled participants. Per MHRI policy and in full alignment with NIH policy, all data compiled from this and future projects related to data collected in this study will be available upon request by any academic or government researcher, with data shared via existing pathways built to ensure transparency but protect participants. As part of the NIH data sharing directive, de-identified data from this study will be transferred to the PCRC De-Identified Data Repositories.

RECORD RETENTION

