- All de-identified data that are collected and entered will remain in the PCRC Data Repositories indefinitely. This de-identified information could be used for future research studies or distributed to other investigators for future research studies without obtaining additional informed consent from you or your legally authorized representative. All future data analysis will be performed on de-identified data in the PCRC Data Repositories. When information and data resulting from this study is presented at scientific meetings or published in a scientific journal, your identity will not be revealed. Quantitative and qualitative data will be presented in aggregate reports and only anonymous excerpts from qualitative data will be used.

Baseline/Time of Enrollment

- 1. In the last week, how would you report your average level of pain with 0 being no pain and 10 being the worst possible pain
- 2. Do you currently take opioid pain medications on an "As Needed" basis as prescribed by your doctor to help manage your pain?
- 3. In the last week, how satisfied have you been with your overall pain management (0 being extremely dissatisfied and 10 being extremely satisfied)
- 4. PROMIS Pain Interference Short Form (see below)

At the end of Weeks 1 and 2

- 1. In the last week, how would you report your average level of pain with 0 being no pain and 10 being the worst possible pain
- 2. If you currently take opioid pain medications on an "As Needed" basis as prescribed by your doctor to help manage your pain, how many doses have you taken in the last week?
- 3. In the last week, how satisfied have you been with your overall pain management, including use of the virtual reality headset (0 being extremely dissatisfied and 10 being extremely satisfied)
- 4. PROMIS Pain Interference Short Form (see below)

At the end of Week 3

- 1. In the last week, how would you report your average level of pain with 0 being no pain and 10 being the worst possible pain
- 2. If you currently take opioid pain medications on an "As Needed" basis as prescribed by your doctor to help manage your pain, how many doses have you taken in the last week?
- 3. In the last week, how satisfied have you been with your overall pain management, including use of the virtual reality headset (0 being extremely dissatisfied and 10 being extremely satisfied)
- 4. PROMIS Pain Interference Short Form (see below)

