- 5. In the last week, how would you report your average level of pain with 0 being no pain and 10 being the worst possible pain
- 6. If you currently take opioid pain medications on an "As Needed" basis as prescribed by your doctor to help manage your pain, how many doses have you taken in the last week?
- 7. In the last week, how satisfied have you been with your overall pain management, including use of the virtual reality headset (0 being extremely dissatisfied and 10 being extremely satisfied)
- 8. PROMIS Pain Interference Short Form (see below)
- 9. Did you find the VR program easy to use (yes/no)?
- 10. How much did you enjoy the VR program (0 being not at all and 10 being very much)?
- 11. While you were using the VR headset, how immersed did you feel in the virtual environment. Alternatively, to what extent did you feel like you "went into" the virtual environment (0 being not at all and 10 being very much)?

- 12. Do you prefer a virtual environment in which you are mostly observing the world around you, or in which you can participate, move around, or engage in activities (active or passive)?
- 13. Do you prefer a virtual environment that is realistic, such as a video of a real location, or simulated, such as computer-generated graphics (realistic or simulated)?

Data collected from electronic health records:

- 1. Participant demographics
 - a. Age
 - b. Sex
 - c. Race
 - d. Ethnicity
- 2. Medical history
 - a. Cancer type
 - b. Time since diagnosis
 - c. Analgesic use (on opioids at baseline (Y/N); if yes, if taking short-acting, longacting, or both; average daily oral morphine equivalents used at the time of enrollment (accounting for the week prior to enrollment) and for the duration of the study period. Daily OMEs will be reported as weekly averages.

PROMIS Item Bank v1.0 - Pain Interference - Short Form 6b

Pain Interference – Short Form 6b

Please respond to each item by marking one box per row.

In the past 7 days...

	-	Not at all	A little bit	Somewhat	Quite a bit	Very much
PAININ3	How much did pain interfere with your enjoyment of life?		2		4	5
PAININ8	How much did pain interfere with your ability to concentrate?		2	3	4	5
PAININ9	How much did pain interfere with your day to day activities?		2	3		5
PAININ10	How much did pain interfere with your enjoyment of recreational activities?		2	3	4	5
PAININ14	How much did pain interfere with doing your tasks away from home (e.g., getting groceries, running errands)?		2 2		4	5

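### The satisfaction question changes wording when VR starts, and distress and well-being are never measured, so Hypothesis 1 cannot be fully evaluated as written

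*Combined protocol and SAP*

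**What the plan says.** All references are to the combined protocol and SAP.

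- **Aims and Hypotheses, Hypothesis 1** lists, besides pain scores, "satisfaction with pain management, lower distress, greater well-being, and lower as-needed opioid use compared to their baseline".
- **Baseline survey, item 3** asks "how satisfied have you been with your overall pain management (0 being extremely dissatisfied and 10 being extremely satisfied".
- **Surveys at the end of Weeks 1 and 2, item 3, and at the end of Week 3, items 3 and 7** ask "In the last week, how satisfied have you been with your overall pain management, including use of the virtual reality headset", with the same recall period and the same 0–10 anchors.
- **Study Design and Methods, secondary outcomes** names "satisfaction with VR intervention and overall pain management (collected weekly". The Data Collection Plan table has a matching entry at the end of each week: "Satisfaction with VR intervention and overall pain management".
- **Data Analysis** compares each "time point (end of weeks 1, 2, and 3) to the baseline (beginning of week 1) regarding pain score and PROMIS survey outcomes". It also says that satisfaction with the VR intervention will be summarised descriptively.
- **Week 3 survey, items 9 to 11** ask about ease of use, enjoyment ("How much did you enjoy the VR program (0 being not at all and 10 being very much") and immersion, once only.

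**The concern.** The study has one group and no blinding, so every statement about effect is a comparison with the participant's own baseline. Such a comparison needs the same question at both ends. For satisfaction, the question gains an explicit prompt about the headset at the moment the headset is introduced. A participant who likes the headset may score higher because the question now points to it, and one who dislikes it may score lower. There is no control group in which a wording effect could be seen on its own.

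Three further gaps affect the same hypothesis. Satisfaction with VR, which Aim 3 also needs, has no separate weekly score. The analysis section states no test of satisfaction against baseline. Distress and well-being are hypothesised to improve, but no instrument is attached to either.

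What is at stake is the interpretation of a secondary outcome and its possible later use. The protocol says: "Results of this study will be used to determine the effect size, variance and variability to estimate sample size for a larger study". It does not say that satisfaction will be used in this way. If it were, the effect size carried forward would include any wording effect.

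**Working it through.** **Step 1. Match each endpoint to its measurement.** The sources are the outcomes paragraph in Study Design and Methods, the Data Collection Plan, the survey items, the list of health-record fields and the PROMIS form.

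| Hypothesis 1 endpoint | Time points measured (of 4) | Same wording as baseline at follow-up | Paired test against baseline stated |
|---|---|---|---|
| Pain score | 4 | 3 of 3 | Yes |
| Satisfaction with pain management | 4 | 0 of 3 | No |
| Distress | 0 | – | No |
| Well-being | 0 | – | No |

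As-needed opioid use, also in Hypothesis 1, is outside this point. Distress otherwise appears only in the Background, and well-being appears nowhere else. PROMIS Pain Interference 6b is a separately named outcome and is not designated as a measure of either. Its item on enjoyment of life asks how far pain interfered, so it contributes to a pain-interference score.

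**Step 2. Which satisfaction comparisons are affected.** There are three comparisons with baseline (Weeks 1, 2 and 3), and all three cross the change of wording. There are three comparisons among the follow-up weeks (1 v 2, 1 v 3, 2 v 3), and all three use constant wording. A change score can be calculated because the scale and recall period match. The difficulty is in what it means.

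**Step 3. VR satisfaction.** At 0 of 3 weekly calls does VR satisfaction receive its own score. Week 3 items 9 to 11 cover it in part, at one time point.

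**Step 4. How large a shift would matter.** The plan gives no significance level and no SD for satisfaction, so there is no figure to reproduce. Assume a paired t-test at two-sided 0.05, the first of the two tests that the plan names for its other outcomes. The smallest observed mean change that reaches significance, in units of the SD of the within-person change, is t(0.975, n−1)/√n:

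- n = 60 (planned): 2.001/7.746 = 0.258 SD
- n = 30 (the stated floor): 2.045/5.477 = 0.373 SD

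In points on the 0–10 scale, over an assumed range of SDs:

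| Assumed SD of change | n = 60 | n = 30 |
|---|---|---|
| 2 points | 0.52 | 0.75 |
| 2.5 points | 0.65 | 0.93 |
| 3 points | 0.77 | 1.12 |

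With no true change, a wording shift of this size would be enough to produce a nominally significant result. The shift needed to hide a real change depends on that change. At n = 60, a true change of 0.30 SD falls below the threshold with an opposing wording effect of just over 0.30 − 0.258 = 0.042 SD. A true change of 0.80 SD would survive an opposing effect of 0.26 SD, because 0.80 − 0.26 = 0.54 SD is still above 0.258.

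**The case against.** The strongest reply is that the added words only clarify. VR is given on top of usual pain management, so once it is in use it is reasonably part of overall pain management. People who already use VR are excluded, so the phrase would have had nothing to refer to at baseline. This makes a large wording effect less obvious. It does not remove the problem, because only the follow-up item directs the respondent to the headset.

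Other objections have some force:

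- **The thresholds are generic.** They would apply to any bias in any paired outcome, and the plan states no such test for satisfaction. This is right. They show what size of shift would matter, not how large the wording effect is. Only the counts in Steps 1 to 3 come from the documents.
- **The combined phrase for satisfaction could denote one merged element.** That reading is possible for the outcomes paragraph and the table. It sits poorly with the analysis section, which promises a summary of VR satisfaction by itself.
- **Distress and well-being look like leftover wording.** They probably are, and no planned analysis is corrupted by them. A stated hypothesis is still left without data.
- **Constant wording does not remove all prompting.** The weekly phone script mentions the headset before any question is asked, so some prompting remains.

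**Conclusion.** The concern holds and should be fixed. All three comparisons of satisfaction with baseline mix a VR effect with a wording effect, and the documents offer no way to separate them. VR satisfaction has no weekly score of its own. Distress and well-being are measured at 0 of 4 time points, so nothing can be reported on them. The missing test for satisfaction is a gap in specification that the same edit closes.

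The size and direction of the wording effect are unknown. If the SD of change is 2 to 3 points (an assumption), a shift of 0.52–0.77 points at n = 60, or 0.75–1.12 points at n = 30, would by itself reach two-sided 0.05 in a paired t-test. The damage is confined to secondary parts of Hypothesis 1 and to the VR satisfaction summary. The primary pain score, PROMIS and the satisfaction contrasts among Weeks 1, 2 and 3 are not affected.

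**What to change.** 1. Ask the baseline satisfaction item word for word at the end of Weeks 1, 2 and 3.
2. After it, add a separate 0–10 item at each of these calls on satisfaction with the VR intervention, summarised descriptively for Aim 3. Placing it second keeps it from prompting the satisfaction rating.
3. Add satisfaction to the paired comparisons with baseline in Data Analysis. This adds 3 comparisons to the 6 already planned (2 outcomes × 3 weeks), so say that they are secondary and how multiplicity is regarded.
4. Remove distress and well-being from Hypothesis 1. If they are kept, name an instrument for each, measure both at all four time points, and add them to the outcomes, the Data Collection Plan and the analysis.

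The cost is one extra question per weekly call (3 per participant) and the deletion of two phrases. If participants are already enrolled, record which wording each was asked. Base the change from baseline on those asked constant wording, and show the others descriptively with the wording disclosed. This reduces the number available for that one comparison. Constant wording removes only the wording effect; the usual limits of an uncontrolled before-after comparison remain.
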